### *Secondary Endpoints*

Multiple secondary endpoints are prespecified for this trial. Secondary endpoints are collected for 16 weeks following randomization:

- a) Overall quality of life as measured by the Schwartz Outcome Scale-10 (SOS10). The SOS10 has ten questions scored on a 0 (never) to 6 (all or nearly all of the time) scale. A total score is computed as the sum across the 10 questions. If two questions are missing, a mean score can be imputed for the missing values to generate a total score. No further imputation will be used for this score. This is self-reported and captured at the 16-week follow-up call.
- b) Linkage to MOUD provider, defined as attending at least one visit with a MOUD provider after discharge, assessed by self-report at 16-week follow-up call.
- c) Self-reported buprenorphine-naloxone (or naltrexone) prescriptions filled (number filled) at the 16-week follow-up call.
- d) Any recurrent opioid use reported at the 16-week phone call follow-up.
- e) Number of recurrent opioid uses reported at the 16-week phone call follow-up.
- f) Number of ED visits or readmissions to VUH 16 weeks post discharge identified in the electronic medical record.
- g) Hospital and emergency department free days
  - a. Hospital free days will be calculated as a count of whole days during the 16 weeks the subject is not in the hospital. If the subject dies before the end of 16 weeks, hospital free days will be equal to -1.
  - b. Hospital and emergency department free days will be calculated as a count of whole days during the 16 weeks the subject is not in the emergency department or in the hospital. If the subject dies before the end of 16 weeks, emergency free days will be equal to -1.
- h) Any overdose reported at the 16-week phone call follow-up.
- i) Death in hospital or documented at the 16 week follow up or in the medical record.
- j) Costs of care, defined as total costs for all care episodes at VUMC 16 weeks post discharge.

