### *Main Analysis*

The primary outcome variable (hospital index length of stay) will be compared between groups using an adjusted generalized linear model. Since the data are positive and may be skewed, like a gamma distribution, we may use a negative inverse link function, a proportional odds model, or transform the data.

In this analysis, group assignment is the main predictor variable. For drawing conclusions about the effect of the Bridge clinic, a critical p-value of 0.05 for the effect of treatment group assignment on the primary outcome will be used. The model will be adjusted for age, race, ethnicity, and area deprivation index. The influence of continuous variables will be assessed using restricted cubic splines with a minimum of three knots. We do not expect missingness in our primary outcome. If there are missing covariates, cases will not be excluded; we will use multiple imputation with predictive mean matching for missingness in adjusting covariates.

Secondary and implementation outcomes will be compared between study groups using adjusted generalized linear models, just as for the primary endpoint. Binary endpoints will use a logit link function. For counts, such as number of medication refills, either a zero-inflated Poisson or a negative binomial model will be fit.

Exploratory outcomes for OPAT patients will not be compared between study groups but will be reported by study group.

There may be missingness in secondary or implementation outcomes. If there are missing outcomes, these may be imputed if they occur in less than 5% of cases. Otherwise, the cohort for which the outcome is available will be described, along with the results of the model evaluating treatment effects in this cohort. All model results will be summarized with point estimates and 95% confidence intervals (CIs), which will be emphasized over p-values when reporting the results for secondary and implementation outcomes. No adjustments for multiplicity will be made.

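### The SAP's overdose endpoint can leave out a fatal overdose, and its missing-data rule does not separate known deaths from non-response

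*SAP*

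**What the plan says.** Six endpoints under SAP, Secondary Endpoints, rest on the 16-week call:

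- a, SOS10: "This is self-reported and captured at the 16-week follow-up call", with the limit that "No further imputation will be used for this score" beyond the allowance for two missing questions.
- b, linkage: "assessed by self-report at 16-week follow-up call".
- c, fills: "prescriptions filled (number filled) at the 16-week follow-up call".
- d, recurrent use: "Any recurrent opioid use reported at the 16-week phone call follow-up"; item e, the number of uses, has the same source.
- h, overdose: "Any overdose reported at the 16-week phone call follow-up".

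None of the six says how to score a patient who died before the call. Two other items do deal with death. Item g states: "If the subject dies before the end of 16 weeks, hospital free days will be equal to -1". Item i makes death an endpoint in its own right and accepts the hospital, the 16-week follow-up and the medical record as sources.

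For missing secondary outcomes, Main Analysis says: "If there are missing outcomes, these may be imputed if they occur in less than 5% of cases". Otherwise the patients with the outcome available are described and analysed. Death is not distinguished from failure to reach the patient. Protocol section 6.0 lists both overdose and death as 16-week endpoints and names the medical record and state-mandated reporting systems among the data sources.

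**The concern.** A fatal overdose is the most severe form of the event in item h, yet the person concerned cannot report it by telephone. Read literally, item h needs a report at the call, so a fatal overdose found only in records does not meet the definition. The SAP is narrower here than the protocol, and the part it loses is the part a reader would most want counted.

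The missing-data rule then leaves the handling of a known death to depend on how many other patients could not be reached. The same death could be imputed as no overdose or no recurrent use, or removed, while item g places it below every possible day count. If deaths differ between arms, item h no longer compares overdose between the randomized groups, and the other call-based results describe survivors who were reached, without being labelled so.

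**Working it through.** The plan states no figure for this point, so there is none to reproduce. The gap is shown by reading the definitions together; the arithmetic only indicates size.

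**1. Fatal overdose on the record, followed through the SAP.** Item i: counted as a death. Item g: scored -1, below the possible range of 0 to 112 days (16 × 7). Item h: no report at the call, so it is missing, or is read as no overdose reported. The SAP does not say which.

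**2. The 5% rule.** The planned total is 336 (SAP, Sample Size Considerations). 5% × 336 = 16.8, so fewer than 5% means at most 16 missing (16/336 = 4.8%; 17/336 = 5.1%), deaths and unreached survivors together. At assumed 16-week death rates:

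| Assumed death rate | Deaths of 336 |
|---|---|
| 1% | 3.4 |
| 2% | 6.7 |
| 3% | 10.1 |
| 5% | 16.8 |

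At 1% to 3%, deaths use part of the allowance of 16; at 5% they fill it. Below the threshold, imputation is allowed for b, c, d, e and h. At or above it the patient is dropped. For SOS10 only dropping is possible, because item a bars further imputation.

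**3. Illustration for item h.** All rates are assumed; 168 per arm, every survivor reached.

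- Non-fatal, each arm: 168 × 6% = 10.08.
- Fatal: 168 × 1% = 1.68 in one arm, 168 × 3% = 5.04 in the other.
- All overdoses: 11.76 v 15.12.

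| Handling of fatal events | Arm with 1% fatal | Arm with 3% fatal | Risk ratio |
|---|---|---|---|
| Counted | 11.76/168 = 7.0% | 15.12/168 = 9.0% | 0.78 |
| Dropped | 10.08/166.32 = 6.06% | 10.08/162.96 = 6.19% | 0.98 |
| Read as no overdose | 10.08/168 = 6.0% | 10.08/168 = 6.0% | 1.00 |

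With 0.5% v 2% fatal the counts are 10.92 v 13.44 (risk ratio 0.81), again shown as 10.08 v 10.08. With equal fatal rates of 1% the ratio stays 1.00, but 1.68 of 11.76 events per arm (14%) are lost.

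**4. Against sampling error.** With fatal events counted, the standard error of the log risk ratio is √(1/11.76 + 1/15.12 − 2/168) = 0.373. The 95% interval around 0.78 is about 0.37 to 1.62. Moving from 0.78 to 0.98 shifts the log ratio by 0.23, about 0.6 of a standard error.

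**5. An extreme assumed case.** With 17 v 14 non-fatal and 0 v 6 fatal overdoses, dropping deaths gives (17/168)/(14/162) = 1.17; counting them gives (17/168)/(20/168) = 0.85. The direction reverses.

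**The case against.** The strongest reply is that the death is not hidden. Item i compares deaths by arm, item g gives them the worst value, the SAP reports missingness for each variable, and the cohort with available data is to be described. This stands. A reader might infer that an arm with more fatal overdoses would look safer in the trial as a whole; that is so only for item h read alone.

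Second, items d, e and h say only that the event is reported at the call, whereas a to c are expressly self-report. A relative who answers might report a fatal overdose. The wording does not exclude this, but the SAP describes no proxy procedure, so the event can be lost rather than must be.

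Third, imputation is optional and narrow. If, say, 60% of patients were reached, about 40% would be missing and the imputation branch would be closed; non-response would then be the larger problem. This also stands, and makes dropping the more likely route.

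Three stronger readings are tempting and fail:

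- That a deceased patient could be given an imputed SOS10 score: item a forbids it.
- That all six outcomes are undefined after death: this fits only quality of life at 16 weeks. A visit, a fill, opioid use or an overdose before death did or did not happen; it was just not collected by interview.
- That SOS10 must score death as worst: this is a choice of estimand. Under assumed mortality of 4% v 1% with equal survivor distributions and all survivors reached, simulation moved the rank-sum z by 0.48; with 2% v 1% by 0.16; with equal mortality not at all.

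**Conclusion.** The point holds for the overdose definition and for the missing-data rule. As written, item h can omit a fatal overdose that the trial already knows about, and Main Analysis lets a known death be treated as ordinary non-response on items b to e and h. It is a point about secondary endpoints; index length of stay is unaffected.

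Its size cannot be taken from the documents, which give no death, overdose or call-completion rates. Under the assumed rates above, a risk ratio of 0.78 to 0.81 would be reported as 0.98 to 1.00. That is well inside sampling error at 168 per arm, so the case rests on the endpoint measuring what its name says more than on a likely change of conclusion.

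A reader might also infer that incomplete calls make the lost fraction larger. They do not: in the two fatal-rate scenarios above, fatal events are 17% to 25% of all overdoses whatever the reach. With 60% of survivors reached they become 26% to 36% of known overdoses, only because fatal events are assumed fully known and non-fatal ones are not.

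**What to change.** Amend the SAP before unblinding; its Introduction says that it was prepared ahead of final data collection and unblinding.

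1. **Item h.** Define the event as an overdose reported at the call, or a death within the 16-week window attributed to overdose in the sources already used for item i and named in protocol section 6.0. Apply the same search and attribution in both arms, without reference to allocation. Show fatal and non-fatal counts separately, since the two are not ascertained equally when calls are incomplete. Add overdose-or-death as a sensitivity analysis where cause is unknown.
2. **Main Analysis.** State that patients known to have died are not imputed on any call-based endpoint. Report deaths by arm beside each of items a to e and h. Label the results for a to e as being among survivors reached.
3. **Limits.** A worst-rank SOS10 analysis may be added, as a sensitivity analysis only. Do not score linkage for deceased patients from VUMC visit records alone: Bridge Clinic visits take place at VUMC and control patients are referred to community care, so such scoring could favour the Bridge arm.

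The cost is a few sentences, a little code and one more abstracted item. Item i records death but not its cause, so cause must be abstracted for each death and will sometimes remain unknown. No further patients or contacts are needed.

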1.0 Study Summary

Title: Evaluating the Impact of the Bridge Clinic in Patients with Opioid Use Disorder

Study Aims:

- Aim 1: To determine whether referral to the Bridge Clinic reduces overall index hospital length of stay when compared to direct referral to a long-term outpatient addiction provider for patients with active opioid use disorder (OUD) being considered for medications-for-addiction treatment (MAT).
- Aim 2: To evaluate the effects of the same intervention in the same population on secondary outcomes including costs, care-linkage, readmission rates, self-reported buprenorphine or naltrexone fills, rate of known recurrent opioid use, and measures of overall quality of life.
- Aim 3: Evaluate fidelity outcomes including Bridge Clinic acceptance and attendance rates among those referred to Bridge Clinic and reasons why patients were not considered to be eligible for inclusion.
- Aim 4: Among the subgroup of patients with an infection for which a course of IV antibiotics is required, additionally evaluate whether access to the Bridge Clinic facilitates outpatient management of the antibiotic therapy, with consequent improvement in clinical (infection and mortality) and resource (inpatient days, time to discharge following a negative blood culture) outcomes.

Study Hypotheses:

- Primary: Among patients with active OUD being considered for MAT, index hospital length of stay will be shorter among patients randomized to referral to the Bridge Clinic than among patients randomized to no referral to the Bridge Clinic.
- Secondary: Among patients with active OUD being considered for MAT, total costs, readmission rates, and rate of recurrent opioid use will be lower while successful care-linkage, self-reported buprenorphine or naltrexone prescription fill rates and quality of life will be higher among patients randomized to referral to the Bridge Clinic than among patients randomized to no referral to the Bridge Clinic.
- Exploratory: Among patients with active OUD being considered for MAT who also have an infection requiring IV antibiotics, referral to the Bridge Clinic will result in lower resource use without worse clinical outcomes when compared with not being referred to the Bridge clinic.

Study Population: Inpatients with OUD being considered for medications-for-addiction treatment (MAT) who have not previously utilized Bridge Clinic.

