To complete these aims, patients admitted to VUH with OUD and being considered for MAT, who have not previously utilized Bridge Clinic, will be enrolled in a pragmatic, single-center, randomized, controlled trial comparing referral to Bridge Clinic versus no referral to usual care in the community. Randomization ratio will be set to ensure the Bridge Clinic is functioning at capacity and the remaining patients will serve as the control. For example, if there is an average of five available slots for new referrals to the Bridge Clinic in a week, and there is an average of 20 eligible patient discharges in a week, the randomization ration will be set as 1:3.

If the Bridge Clinic is successful in bridging buprenorphine-naloxone use (as well as IM naltrexone in some cases) and linking to additional care, it is expected to decrease the overall length of stay of patients with OUD who are initiating buprenorphine-naloxone therapy. This reduction in length of stay for these patients will reduce costs and increases bed availability for other patients while simultaneously providing these patients with the care they need.

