6.0 Study Procedures

An enrolled patient will receive a referral to social work for “outpatient MAT”. The ACT social worker will approach the patients with resources for outpatient MAT determined by randomization (though the social worker can escalate patients in either condition to a higher level of care as appropriate after randomization). All patients will be offered usual information about outpatient MAT. Patients randomized to be eligible for referral to the Bridge Clinic will additionally receive information about the Bridge Clinic and this will be offered as an option during discussion of the plan for MAT. Patients who are randomized to not being offered a Bridge Clinic referral will not receive information about the Bridge Clinic and the Bridge Clinic will not be offered as an option.

Subsequent to comparator group assignment, patients will be followed to measure outcomes. All data will be captured from the medical record, financial systems, state-mandated reporting systems, and from other standard of care documentation. The data elements to be collected include the following:

Baseline demographics collected at time of enrollment

- Age
- Gender
- Race
- Ethnicity
- SES indicators

Primary Endpoint

- Overall index hospital length of stay

Principal Investigator: [name]

Version Date: April 7, 2022

Study Protocol: Evaluating the Impact of the Bridge Clinic in Patients with Opioid Use Disorder

Additional Endpoints collected for 16 weeks following randomization

- Costs of care (total costs, and costs for each admission and care resource used (e.g. Bridge Clinic))
- Linkage to MAT provider (attending at least one visit with a MAT provider)
- Self-reported buprenorphine-naloxone (or naltrexone) prescriptions filled
- Readmission
- ED visits
- Hospital and ED free days
- Recurrent opiate use
- Overall quality of life as measured by the Schwartz Outcome Scale-10 (SOS10)
- Overdose
- Death
- Cross-over to Bridge Clinic to community care or vice-versa

Additional Endpoints for patients with infection suitable for outpatient management, collected for 16 weeks following randomization

- New, persistent, or recurrent infection (as defined by a positive culture and/or change in antibiotic regimen)
- Completion of antibiotic therapy
- Days from negative blood culture to first hospital discharge

Implementation Measurements

- Acceptance of Bridge Clinic as a bridging provider
- Reasons for ineligibility

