12.0 Follow-up and Record Retention

The initial study is anticipated to progress from initiation to completion in about 12 months. For each participant, the study will commence at enrollment and last until 16 weeks from randomization. Patient clinical outcomes will be collected. Identified data in the secure database will be stored consistent with record retention requirements, typically 5 years from completion of the research. De-identified dataset will be maintained for secondary analyses and to support the reproducibility of reports.

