## **Introduction**

To improve care for patients with opioid use disorder (OUD), Vanderbilt has implemented an Addiction Consult Team (ACT) and a Bridge Clinic. The primary purpose of the Bridge Clinic is to facilitate discharge for inpatients who are being considered for medications for OUD (MOUD). Specifically, the Bridge Clinic provides patients with temporary access to treatment at an outpatient clinic while they are waiting to be accepted into a long-term clinic. This document describes the statistical analysis plan for a pragmatic, single center, randomized, controlled trial designed to evaluate the impact of the Bridge Clinic on improving care for patients with active OUD. This document has been prepared prior to final data collection and unblinding. Because inpatient providers may delay discharge for patients with OUD who lack a source of outpatient care for MOUD, it is hypothesized that OUD patients referred to the Bridge Clinic will have a decreased overall length of stay, will follow up with their Bridge Clinic provider, and will have a reduction in overall costs for care.

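### SAP cost endpoint (j) starts its 16 weeks at discharge, not randomization, and as written leaves the index stay out of a total-cost hypothesis

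*SAP*

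**What the plan says.** Item (j) of the SAP's Secondary Endpoints is "Costs of care, defined as total costs for all care episodes at VUMC 16 weeks post discharge". The line introducing the same list says "Secondary endpoints are collected for 16 weeks following randomization".

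The protocol agrees with that introductory line. Section 6.0 places costs under the heading "Additional Endpoints collected for 16 weeks following randomization" and asks for total cost as well as a breakdown by admission and by type of service, naming the Bridge Clinic as an example. Section 12.0 says that for each participant "the study will commence at enrollment and last until 16 weeks from randomization".

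The hypothesis is about the whole cost. The secondary hypothesis in Protocol section 1.0 is that "total costs, readmission rates, and rate of recurrent opioid use will be lower" in the Bridge Clinic arm, and the SAP Introduction says referred patients "will have a reduction in overall costs for care". Protocol section 3.0 gives the mechanism: "This reduction in length of stay for these patients will reduce costs".

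**The concern.** Patients are randomized as inpatients (Protocol section 5.0; SAP Interventions), so the two starting points differ by the rest of the index stay. That is the stretch of care the intervention is meant to shorten.

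A window that opens at discharge excludes the main expected saving. It still counts the cost of Bridge Clinic visits, which are VUMC care, and any change in VUMC readmissions and ED visits. The analysis would then test only the post-discharge part of the cost hypothesis. Protocol sections 3.0 and 7.0 link the results to sustaining or expanding the clinic, so a cost result that misses the bed-day saving could mislead that decision.

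**Working it through.** The documents give no sample size, power or effect size for costs, so there is no cost figure to reproduce. The check compares the windows and then counts days.

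**Inputs.** Target reduction in stay 1.5 days; 168 patients per group; mean stay 9 days; log-scale mean ln(5.5) and SD ln(2.7) (all Protocol section 10.0, Interim Analysis). Follow-up is 16 × 7 = 112 days.

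**Index days counted for a 9-day stay.** The documents do not give the day of randomization; day 0 to day 5 is assumed.

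| Reading | Window | Index days counted |
|---|---|---|
| (j) taken literally | discharge to discharge + 112 | 0 |
| SAP introductory line and protocol | randomization to randomization + 112 | 9 to 4 |
| Index stay plus 16 weeks | admission to discharge + 112 | 9 |

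**Bed-days left out by literal (j).** Assignment can only affect days after randomization, so the whole reduction belongs in a window that starts there.

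- 1.5 × 168 = 252 bed-days in the Bridge arm.
- 1.5 / 9 = 16.7% of the mean stay.

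**If the 1.5 days applies to the geometric mean (5.5 to 4.0 days).** This assumes lognormal stays and a multiplicative effect.

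- Implied arithmetic mean: 5.5 × exp(ln(2.7)² / 2) = 9.007 days, in agreement with the 9 days in the protocol.
- Reduction in the mean: 9.007 × (1.5 / 5.5) = 2.46 days per patient.
- 2.4565 × 168 = 413 bed-days.

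**Sign of the cost difference.** Let N be the difference (Bridge minus control) in mean post-discharge VUMC cost per patient, chiefly Bridge Clinic cost less any saving on readmissions and ED visits. Let d be the cost of one index bed-day. Ignoring the small shift in where the windows end:

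- literal (j) compares N;
- the total-cost hypothesis concerns N − 1.5d.

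The signs differ when 0 < N < 1.5d (upper limit 2.46d under the lognormal assumption). In bed-day equivalents:

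| N | Literal (j) | Index stay included |
|---|---|---|
| −1.5 | −1.5 | −3.0 |
| 0 | 0 | −1.5 |
| 0.5 | 0.5 | −1.0 |
| 1.5 | 1.5 | 0 |

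With equal post-discharge costs, literal (j) shows no difference, although total cost has fallen by 1.5 bed-days per patient.

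**Index stay plus 16 weeks.** Here the saving is captured. The arms' windows differ in length by about 1.5 / 112 = 1.3% (2.46 / 112 = 2.2%).

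**The case against.** The strongest reply is that item (j) can be read as everything from the index admission to 16 weeks after discharge. It refers to all episodes of care, the introductory line starts at randomization, the protocol wants costs by admission, and nothing says index costs are excluded. On that reading only the 1.3% mismatch remains. The reading is possible, but it is not the natural one. Item (f) in the same list uses the same post-discharge phrase for readmissions, where it can only mean care after discharge, and no text adds index costs to (j).

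Several further points stand:

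- Reversal is not shown to be likely. The protocol also expects fewer readmissions, so N may be negative, and the documents give no cost per day, clinic cost or readmission rate.
- N is a difference in means. The SAP allows a transformed or proportional odds model, and the sign of that coefficient need not follow the condition above. The omission of index costs does not depend on the model.
- Bed-days are not money, and 16.7% is a share of stay, not of 16-week cost.
- The bed-day effect is still visible in the primary endpoint, and in hospital-free days if those are counted from randomization. Costs are one of ten lettered secondary endpoints, for which the SAP emphasizes estimates and intervals over p-values.
- Item (j) covers VUMC care only, so even a corrected version omits community care.

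These points limit the consequences. They do not reconcile (j) with its own introductory line or with the protocol.

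**Conclusion.** The concern holds. Item (j) conflicts with the sentence that governs it and with Protocol sections 6.0 and 12.0. Followed as written, it leaves the total-cost hypothesis without its index-stay component. At the planning target that is 252 bed-days across 168 Bridge patients, or about 413 if stays are lognormal and the effect is multiplicative. The cost result has the wrong sign if net post-discharge cost lies between zero and the cost of the index days saved; the documents do not allow the chance of that to be judged.

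The conclusion about omitted cost rests on the literal reading. Under the looser reading the defect is small, but the SAP would still need to state it. The primary analysis is unaffected. This should be fixed before unblinding.

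**What to change.** Redefine item (j) as total VUMC costs from randomization through day 112, including the index admission. Establish, blinded to allocation, whether the financial data can be split at the randomization date. If so, count the post-randomization part of the admission; if not, count the whole admission. Write the choice into the SAP. Pre-randomization cost is balanced between arms in expectation, so including it adds noise but no bias.

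Report index-stay, readmission/ED and Bridge Clinic costs as components, and keep the 16-week post-discharge cost as a supportive result. Item (f) can keep its discharge-based window, which is natural for readmissions, but the SAP should say that the two windows differ.

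The cost is a short SAP edit. The SAP says it was written before final data collection and unblinding, and Protocol section 6.0 already plans costs by admission and service. There are two drawbacks: a patient with a long index stay has less post-discharge time in the window, and using the whole admission reduces precision.
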